## 15. APPENDIX 3 SAS SAMPLE CODES

A sample of the SAS code for sensitivity analysis using the copy-reference MI method is provided as below:

```
/*Generate transpose of adcf - wide format before Step 1*/
/*----- Generates 10 imputed data sets based on original (non-transformed)
data-----*/
/*Step 1: Achieve Monotone Missing Data Pattern */
PROC MI DATA=&DATA SEED=14823 NIMPUTE=10 OUT=MONO;
  /* Use numeric TRT01PN */
  VAR BASE AVAL1 AVAL2 AVAL3; /*Refer to AVAL at Visits 5, 6, and 7*/
  MCMC IMPUTE=MONOTONE NBITER=5000 NITER =5000;
  BY TRT01PN;
  run;

/*Step 2: Achieve Control-Based Copy-Reference Imputation */
PROC MI DATA=MONO SEED=14823 NIMPUTE=1 OUT=OUTM1;
  CLASS TRT01PN;
  By _IMPUTATION_;
  VAR TRT01PN BASE AVAL1 AVAL2 AVAL3;
  MONOTONE REG (AVAL2 AVAL3);
  MNAR MODEL (AVAL1 AVAL2 AVAL3/ MODELOBS = (TRT01PN = '0'));
  /*Control=Placebo*/
  RUN;
PROC SORT DATA =OUTM1; BY _IMPUTATION_ TRT01PN USUBJID LBASE; RUN;
/*Generate transpose of OUTM1 - skinny format before Step 3*/

/*Step 3: Run MMRM Analysis on Imputed Data */
PROC MIXED DATA=OUTM1 METHOD=REML;
  BY _IMPUTATION_;
  CLASS TRT01PN USUBJID AVISITN COUNTRY SEX;
  MODEL CHG = TRT01PN AVISITN COUNTRY SEX TRT01PN*AVISITN BASE / DDFM=KR;
  REPEATED / SUBJECT=USUBJID (TRT01PN) TYPE=UN;
  LSMEANS TRT01PN*AVISITN / CL DIFF PDIFF;
  ESTIMATE 'TRT S - P AT WEEK 24' TRT01PN -1 1
  TRT01PN*AVISITN 0 0 -1 0 0 1 / CL LOWER LOWERTAILED;
  ODS OUTPUT PARAMETERESTIMATES=PESTIMATES;
  RUN;

/*Step 4: Combining estimates from each imputed data set */
/*First, sort the data of estimates by visit (variable "LABEL") */
PROC MIANALYZE DATA=PESTIMATES;
  MODELEFFECTS ESTIMATE;
  STDERR STDERR;
  BY LABEL;
  ODS OUTPUT PARAMETERESTIMATES= MIPARM;
  RUN;
```

A sample of the SAS code for sensitivity analysis using the tipping-point approach is provided as below:

```
/*-----*/
```

```
/*--- Performs multiple imputation analysis ---*/
/*--- for specified shift parameters: ---*/
/*--- data= input data set ---*/
/*--- smin= min shift parameter ---*/
/*--- smax= max shift parameter ---*/
/*--- sinc= increment of the shift parameter ---*/
/*--- outparms= output parameters ---*/
/*-----*/
%MACRO MIPARMS( DATA=, SMIN=, SMAX=, SINC=, OUTPARMS=);
DATA &OUTPARMS;
  SET _NULL_;
RUN;
/*----- # of shift values -----*/
%LET NCASE= %SYSEVALF( (&SMAX-&SMIN)/&SINC, CEIL );
/*--- Multiple imputation analysis for each shift ---*/
%DO JC=0 %TO &NCASE;
  %LET SJ= %SYSEVALF( &SMIN + &JC * &SINC);

  /*--- Generates 10 imputed data sets ---*/

/*Step 1: Achieve Monotone Missing Data Pattern */

  PROC MI DATA=&DATA SEED=14823 NIMPUTE=10 OUT=MONO;
  ** Use numeric TRT01PN ;
  VAR BASE AVAL1 AVAL2 AVAL3; /*Refer to AVAL at Visits 5, 6, and 7*/
  MCMC IMPUTE=MONOTONE NBITER=5000 NITER =5000;
  BY TRT01PN;
  run;

/*Step 2: Impute all visits under MAR first, then apply delta adjustments
at each visit*/

  PROC MI DATA= OUTM1 SEED=14823 NIMPUTE=1 OUT=OUTM2;
  CLASS TRT01PN;
  BY _IMPUTATION_;
  VAR TRT01PN BASE AVAL1 AVAL2 AVAL3;
  MONOTONE REG (AVAL2 AVAL3);
  MNAR ADJUST( AVAL1 / SHIFT=&SJ ADJUSTOBS=(TRT01PN ='1') );
  MNAR ADJUST( AVAL2 / SHIFT=&SJ ADJUSTOBS=(TRT01PN ='1') );
  MNAR ADJUST( AVAL3 / SHIFT=&SJ ADJUSTOBS=(TRT01PN ='1') );
  RUN;
  PROC SORT DATA =OUTM1; BY _IMPUTATION_ TRT01PN USUBJID BASE; RUN;

/*Generate transpose of OUTM2 - skinny format before Step 3*/

/*Step 3: Run MMRM Analysis on Imputed Data */

PROC MIXED DATA=OUTM2 METHOD=REML;
  BY _IMPUTATION_;
  CLASS TRT01PN USUBJID AVISITN COUNTRY SEX;
  MODEL CHG = TRT01PN AVISITN COUNTRY SEX TRT01PN*AVISITN BASE /
  DDFM=KR;
  REPEATED / SUBJECT=USUBJID (TRT01PN) TYPE=UN;
  LSMEANS TRT01PN*AVISITN / CL DIFF PDIFF;
  ESTIMATE 'TRT S - P AT WEEK 24' TRT01PN -1 1
  TRT01PN*AVISITN 0 0 -1 0 0 1 / CL LOWER LOWERTAILED;
  ODS OUTPUT PARAMETERESTIMATES=PESTIMATES;
```

```
RUN;

/*First, sort the data of estimates by visit (variable "LABEL") */

PROC SORT DATA=PESTIMATES; BY LABEL; RUN:

/*Step 4: Combining estimates from each imputed data set */

PROC MIANALYZE DATA=PESTIMATES;
MODELEFFECTS ESTIMATE;
STDERR STDERR;
BY LABEL;
ODS OUTPUT PARAMETERESTIMATES=MIPARM;
RUN;
DATA MIPARM;
SET MIPARM;
SHIFT= &SJ;
RUN;

/*----- Output multiple imputation results -----*/

DATA &OUTPARMS;
SET &OUTPARMS MIPARM;
RUN;
%END;
%MEND MIPARMS;

/*Assume that the tipping point for the shift parameter that reverses the
study conclusion is between 0 and 100. The following statement performs
multiple imputation analysis for each of the shift parameters
0,10,20,30,...,100.*/

ODS LISTING CLOSE;
%MIPARMS (DATA=XXXX, SMIN=0, SMAX=100, SINC=10, OUTPARMS=PARMS1);

/* Step 5: Finding Tipping Point for Shift Parameter between 0 and 100
such that p-value is less than 0.05, below is an example for a tipping
point for the shift parameter between 40 and 50.
For a two-sided Type I error level of 0.05, the tipping point for the
shift parameter is greater than 40. The following statement performs
multiple imputation analysis for shift parameters 40, 41, ..., 50*/

%MIPARMS (DATA=XXXX, SMIN=40, SMAX=50, SINC=1, OUTPARMS=PARM2);
/*The following statements display the p-values that are associated with
the shift parameters.*/
PROC PRINT LABEL DATA=PARM2;
VAR SHIFT PROBT;
TITLE 'P-VALUES FOR SHIFT PARAMETERS';
LABEL PROBT='PR > |T|';
FORMAT PROBT 8.4;
RUN;
```

A sample of the SAS code for van Elteren test is provided as below:

```
proc nparlway data=adef ;  
  strata BLGSTAGE BLITCHRO BLGDIAB;  
  class trt01p;  
  var chg;  
run;
```

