### **Analysis model:**

The complete MI method is described below:

- Impute missing values using the normal distribution specified in the above algorithm to impute values for all participants visit  $t$ . After imputation, all participants in the defined analysis population(s) will have non-missing change from baseline in sBA at visit  $t$ .
- Repeat the imputation for visits  $t+1, \dots, \text{Week 3}$ , until measurements at visits from visit  $t$  to Week 3 are imputed to form a complete dataset.

- Repeat the process  $K$  ( $K=5$ ) times, using the procedure described above to form  $K$  imputed complete datasets.
- Fit the MMRM model including terms for treatment, and all other terms as in the primary analysis model to each imputed dataset, to estimate the change from baseline during at Week 3 and its variance.
- Combine the results from the  $K$  imputed datasets using the SAS procedure MIANALYZE to derive the MI estimator.

We fit the analysis model (MMRM model specified before) to the  $k$ th imputed dataset, denoting the corresponding estimate of the variance  $V_k$ . The MI estimator,  $\tilde{\theta}_{MI}$ , is the average of the  $K$  individual estimators.

The estimated variance of  $\tilde{\theta}_{MI}$  is a combination of the between- and within-imputation variability as follows:  $V_{MI} = W + \left(1 + \frac{1}{K}\right)B$ , where  $W = \frac{1}{K} \sum_{k=1}^K V_k$  is the within-imputation variability and is  $B = \frac{1}{K-1} \sum_{k=1}^K (\tilde{\theta}_k - \tilde{\theta}_{MI})^2$  is the between-imputation variance. The statistic  $T = \frac{\tilde{\theta}_{MI} - \theta}{\sqrt{V_{MI}}}$  has an approximate  $t_V$  distribution

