After such a tipping point is determined, clinical judgment can be applied as to the plausibility of the specifications underlying this tipping point. The tipping point can be identified while the result is no longer statistically significant. This imputation analysis uses a specified sequence of shift parameters, which adjust the imputed values for observations in the active treatment group and independently for the placebo group. A sample of SAS code for sensitivity analysis using the tipping-point method is provided in Appendix 3.

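### The SAP Appendix 3 sample code does not carry out the tipping-point and imputation analyses described in the text: the shift step reads the wrong dataset, only the active arm is shifted, and two of three baseline covariates are missing

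*SAP*

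**What the plan says.** **Tipping-point text.** SAP 6.1.8 sets out seven steps: impute without distinguishing missing-data categories, analyse, combine, then repeat with an increasingly severe shift until the p-value exceeds 0.05. Its closing paragraph says that the shifts "adjust the imputed values for observations in the active treatment group and independently for the placebo group". Protocol 10.4.1.1 (Tipping Point Analysis) says the same of both arms.

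**Tipping-point code (SAP Appendix 3).** Step 1 is "PROC MI DATA=&DATA SEED=14823 NIMPUTE=10 OUT=MONO". Step 2, the only step that applies a shift, is "PROC MI DATA= OUTM1 SEED=14823 NIMPUTE=1 OUT=OUTM2". Each of its three shift lines has the form "MNAR ADJUST( AVAL1 / SHIFT=&SJ ADJUSTOBS=(TRT01PN ='1", which selects the active arm.

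**Where OUTM1 comes from.** It is created once, in the preceding copy-reference program, by "PROC MI DATA=MONO SEED=14823 NIMPUTE=1 OUT=OUTM1" with the placebo-based statement "MNAR MODEL (AVAL1 AVAL2 AVAL3/ MODELOBS = (TRT01PN = '0".

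**Analysis model.** The primary model (SAP 6.1.2; Protocol 10.4.1.1) adjusts for baseline sBA, gestational age and gestational diabetes. SAP 6.1.7 asks that the model fitted to each imputed dataset contain treatment "and all other terms as in the primary analysis model". The model in both Appendix 3 programs is "MODEL CHG = TRT01PN AVISITN COUNTRY SEX TRT01PN*AVISITN BASE / DDFM=KR".

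**Status.** SAP 6.1.7 and 6.1.8 call the code an example or a sample. Protocol 10.4.1.1 (Missing Data) says the SAP will prespecify the full multiple-imputation details, including methodology, number of imputations and seed.

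**The concern.** A tipping-point analysis is informative only if the shift reaches the imputed values. The step that should apply it reads a dataset that the macro never makes. Where that dataset does exist, its missing values have already been filled in from the placebo distribution. That is also not the missing-at-random starting point that the macro's own comment describes.

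The covariate mismatch is a separate problem. These analyses are meant to show how far the primary result depends on the missing-data assumption. If the covariates change at the same time, a difference from the primary result cannot be attributed to that assumption alone.

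If text and code still disagree at unblinding, someone must decide which one governs after the data are visible.

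**Working it through.** **1. Dataset flow in the tipping-point macro**

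| Step | Reads | Writes | State of the data |
|---|---|---|---|
| 1 | the supplied analysis data | MONO | made monotone; later gaps remain |
| 2 (shift) | OUTM1 | OUTM2 | depends on what OUTM1 is |
| 3 (mixed model) | OUTM2 | estimates | |

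MONO is not read again inside the macro. Three situations follow.

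- Macro run alone: OUTM1 does not exist and Step 2 stops.
- Macro run after the copy-reference program, with OUTM1 transposed in place: a comment there puts OUTM1 into long format before the mixed model, and that model reads OUTM1 using CHG and AVISITN. Step 2 needs the wide columns AVAL1 to AVAL3, so it stops unless the transpose kept them.
- A wide, completed OUTM1 still in the session: nothing is missing, so nothing is imputed and nothing is shifted. Both programs use the same model, so every shift returns the copy-reference result.

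The grid has (100 − 0)/10 + 1 = 11 shifts. The refinement from 40 to 50 by 1 also has 11.

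**2. Illustration of the third situation**

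The plan's own figure reproduces. With 100 per arm, difference 10 and SD 25, SE = 25 × √(2/100) = 3.54 and 10/3.54 = 2.83. Two-sided power at 0.05 is 80.7%, against the stated 80%.

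Single simulated datasets then used 100 per arm and SD 25. The following were assumed: true difference 10 or 14, within-participant correlation 0.6, and Week 3 missingness of 5%, 10% or 20%. The documents give no missingness rate; SAP 6.1.2 expects little. Analysis used sequential regression imputation (10 imputations), Week 3 ANCOVA and Rubin's rules, in Python. SAS was not run.

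| True difference | Assumed missing | Missing at Week 3, active/placebo | p at all 11 shifts, wide OUTM1 | p at shift 0, reading MONO | First shift with p > 0.05, reading MONO |
|---|---|---|---|---|---|
| 10 | 5% | 6/8 | 0.0386 | 0.0256 | 20 (p = 0.0760) |
| 10 | 10% | 9/8 | 0.0256 | 0.0147 | 20 (p = 0.1021) |
| 10 | 20% | 22/24 | 0.0315 | 0.0153 | 10 (p = 0.0661) |
| 14 | 5% | 2/4 | 0.0003 | 0.0003 | none by 100 (p = 0.0087 there) |
| 14 | 10% | 8/6 | 0.0003 | 0.0001 | 60 (p = 0.0640) |
| 14 | 20% | 22/20 | 0.0094 | 0.0022 | 20 (p = 0.2249) |

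Reading OUTM1, the p-value never moves. Reading MONO, five of the six datasets have a tipping point within the grid.

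**3. Arms shifted**

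All three shift lines select `TRT01PN='1'`. None selects placebo.

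**4. Covariates**

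| Term | Primary model | Both Appendix 3 programs |
|---|---|---|
| Baseline sBA | yes | yes (BASE) |
| Gestational age | yes | no |
| Gestational diabetes | yes | no |
| Country | no | yes |
| Sex | no | yes, but constant (inclusion criterion 2: all female) |

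One of three baseline covariates is kept and two are missing. The Week 24 label on the contrast and a comment about Visits 5 to 7 do not fit an endpoint at Week 3, which suggests code carried over from another study.

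**The case against.** The strongest reply is that this is sample code. It has placeholders such as a dummy dataset name and a worked example of a tipping point, so nobody would run it unedited. The governing procedure in SAP 6.1.8 is sound. A step that stops with an error is visible and would be corrected.

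Much of this stands, and it rules out four stronger readings that a reader might infer.

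- *The analysis will look robust whatever the data.* Not supported. A flat result needs a wide, completed OUTM1 in the session, which conflicts with the transposition comment. It looks robust only if the copy-reference p-value is at or below 0.05; otherwise every shift is non-significant.
- *The code drops the primary covariates.* Too broad: baseline sBA is in both models.
- *The tipping-point method is defective.* The text describes a workable method; the conflict is between code and text.
- *SAP 6.1.8 prescribes a two-way grid of shifts.* It does not. It calls for independent shifts in the two arms and leaves their combination open.

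It is also fair that the requirement to keep all primary-model terms sits in 6.1.7. For the tipping point, 6.1.8 asks only for standard procedures, so the mismatch there rests on the stated purpose of testing the primary result.

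The sample-code defence still does not dispose of the point. The seed and the shift values appear only in Appendix 3. SAP 6.1.5 points ahead to placebo-based imputation, but no later section of the SAP body describes it; the copy-reference program is its only SAP specification. Given the protocol's commitment to prespecify these details, for those items the appendix is the prespecification.

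**Conclusion.** The point holds as a conflict between code and text that should be corrected. As printed, none of the three situations examined yields the tipping-point analysis of SAP 6.1.8: the shift step fails, or it shifts zero values at every grid point. The placebo shift promised in both documents is absent, and both programs fit a model lacking two of the three primary baseline covariates.

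The dataset trace and the covariate count rest on the documents alone. The claim that nothing is shifted rests on the shift acting only on imputed values, as SAP 6.1.8 describes it. The simulated p-values rest on the assumed correlation and missingness and show the mechanism only; they do not predict this trial's tipping point.

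The effect is confined to supportive analyses. The primary MMRM, the success criterion and the testing hierarchy do not depend on this code.

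**What to change.** Before unblinding, amend SAP Appendix 3 as follows.

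1. In Step 2 of the tipping-point macro, read `DATA=MONO`. The sort that follows also names OUTM1 and should name OUTM2.
2. Add a separate shift parameter for the placebo arm (`ADJUSTOBS=(TRT01PN='0')`), and state in 6.1.8 which combinations of active and placebo shifts will be run.
3. In both mixed-model steps, replace country and sex with gestational age (continuous, so not a class variable) and gestational diabetes (class variable).
4. Relabel the Week 24 contrast as Week 3, and correct the visit comments to Weeks 1 to 3.

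The cost is a few lines of code and a sentence of text. No new data are needed. The placebo shift adds computing runs, but the text already commits to it. A dry run on dummy data, checking that the estimate moves as the shift increases, would confirm the correction.
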